## **Study Design and Methods**

### **I. Subjects:**

#### **A. Overview:**

The proposed study will comprise of two parts: Part I: an observational study based on ecological momentary assessment, and Part II: a randomized partial crossover clinical trial. Same subjects will participate in both parts of the study.

In the observational study, the dietary intake of the subjects will be evaluated using an ecological momentary assessment approach for 7 days. In the randomized partial crossover clinical trial, four test breakfasts will be administered so that each subject will get exposed to only two out of the four diets (thus, partial crossover). Therefore, there will be six possible combinations of diets (i.e.  $4! / 2! [4-2]!$ ) and 12 possible ordered combinations (i.e. permutations;  $4! / [4-2]!$ ) of diets. Four subjects will be randomly assigned to each of these 12 possible ordered combinations of diets. Thus, the total sample size will be 48 (i.e.  $n = 4 \times 12$ ).

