### **Outcome Measures:**

#### **A. Primary Outcome Measures:**

1. Difference of energy intake (kcal) in meals containing eggs as compared to meals that do not contain eggs

Energy intake will be determined using Remote Food Photography Method (RFPM) and the meals of all test subjects will be categorized based on the presence or the absence of eggs in the meals.

[Time Frame: Day 1-7 of the ecological momentary assessment part (Part I) of the study]

2. Difference of energy intake (kcal) in high egg consumers as compared to low egg consumers  
Comparison of mean daily energy intake as measured by Remote Food Photography Method (RFPM) between high egg consumers and low egg consumers identified by providing a food frequency questionnaire (FFQ).

[Time Frame: Day 1-7 of the ecological momentary assessment part (Part I) of the study]

3. Difference of saturated fat (g) intake in meals containing eggs as compared to meals that do not contain eggs

Saturated fat intake will be determined using Remote Food Photography Method (RFPM) and the meals of all test subjects will be categorized based on the presence or the absence of eggs in the meals.

[Time Frame: Day 1-7 of the ecological momentary assessment part (Part I) of the study]

4. Difference of saturated fat (g) intake in high egg consumers as compared to low egg consumers

Comparison of saturated fat intake as measured by Remote Food Photography Method (RFPM) between high egg consumers and low egg consumers identified by providing a food frequency questionnaire (FFQ).

[Time Frame: Day 1-7 of the ecological momentary assessment part (Part I) of the study]

5. Difference of blood glucose levels compared between different test breakfasts

This will be measured on visit 1 and 2 after providing test breakfasts.

[Time Frame: Changes in concentration (area under the curve; AUC) from 30 minutes prior to breakfast to 180 minutes after consumption of test breakfasts (Part II of the study)]

6. Difference of insulin levels compared between different test breakfasts

This will be measured on visit 1 and 2 after providing test breakfasts.

[Time Frame: Changes in concentration (area under the curve; AUC) from 30 minutes prior to breakfast to 180 minutes after consumption of test breakfasts (Part II of the study)]

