**Statistical Analyses Plan (SAP):**

Data will be imported to R statistical software and the distributions will be examined visually to make a decision about the appropriate statistical tests (i.e. parametric / non-parametric) to be used for all comparisons. All statistical analyses will be conducted using R statistical software. Family-wise error rate will be maintained at 0.05.

Free living EI and saturated fat intake during main three meals (i.e. breakfast, lunch and dinner) of each subject will be determined using RFPM and the meals of all test subjects will be categorized based on the presence or the absence of eggs in the meals. Means of EI and saturated fat intake during each main meal will be compared between the two categories (i.e. eggs present vs. eggs absent) using multi-level mixed-effects regression models constructed using the lmerTest package in R statistical software. Age, sex, baseline BMI and / or waist circumference will be included in the models as subject-level covariates.

Based on RFPM data, mean EI and saturated fat intake of the high egg consumers (i.e. individuals in the top quartile based on egg consumption) will be compared with the mean EI and saturated fat intake of the low egg consumers (i.e. individuals in the bottom quartile based on egg consumption) via Welch t-tests or the Wilcoxon test, depending on the distributions of the data.

Linear regression models will be constructed to examined the associations between a) total EI, b) saturated fat intake and c) egg intake and each of i) baseline insulin level, ii) blood glucose level, iii) HOMA-IR, and iv) HbA1C level. The usual regression assumptions will be assessed and any concerns will be ameliorated as appropriate (e.g. apply a transformation as guided by Box-Cox)

Using the data obtained in the randomized partial crossover trial, multi-level mixed effects regression models will be constructed using the lmerTest package in R statistical software to predict each of a) PYY (AUC and pre-post change); b) GLP-1 (AUC and pre-post change); c) ghrelin (AUC and pre-post change); d) blood glucose (AUC and pre-post change); e) insulin (AUC and pre-post change); f) metabolic rate using i) the presence of eggs in the diet; ii) the

presence of a high content of saturated fat in the diet; iii) their interaction. Age, sex, baseline BMI and / or waist circumference will be included in the models as subject-level covariates.

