Several issues question the applicability of the epidemiological observations about egg consumption and diabetes. While eggs improve glycemic control of diabetic individuals under the controlled environment of experimental intervention [11], epidemiological studies indicate that under free living conditions, higher egg intake predicts risk of diabetes or CVD risk for diabetic individuals. Possibly, higher egg intake is simply a marker for other dietary indiscretions. For instance, from lowest to highest egg consumers, men reported greater daily energy intake from 1,870 kcal to 2,372 kcal, greater saturated fat intake and a 5-fold increase in bacon consumption, although their BMIs were nearly identical [3] - this strongly suggests that greater egg intake is associated with greater intake of other nutrients. Predictably, the association of CVD with egg consumption disappeared when bacon intake was also considered [3]. ***Individuals predisposed to impaired glycemic control*** may be particularly susceptible to undesirable health effects of higher saturated fat and energy intake. In such individuals, saturated fat may overwhelm the beneficial effects of eggs on lipid and glycemic profile. A possibility that beneficial effects of eggs on lipids can get counterbalanced is also expressed by Hu et al. [3]. For a clearer understanding in those with impaired glycemic control, the effect of eggs should be separated from that of accompanying saturated fat consumed.

Therefore, our ***Central hypothesis*** is that the association of egg intake with increased CVD risk in diabetics, or with greater risk of developing diabetes, is due to the accompanying dietary pattern, and not due to eggs per se. Specifically, we postulate that rather than eggs, the greater energy intake and saturated fat intake (e.g. bacon, butter, hash browns, etc.) associated with ***greater*** egg consumption contribute to the stated health risks. We propose to test this hypothesis as follows, by using the remote food photography method (RFPM), which was developed and validated by our co-investigator (CM). RFPM employs smartphone technology as a means of estimating energy intake remotely from participants' home environments.

**Aim: Use the RFPM to accurately determine the dietary pattern associated with egg intake in 40 free living non-diabetic individuals who eat eggs often.**

This aim will test the following hypotheses:

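### Primary outcomes 2 and 4 compare self-selected high and low egg consumers without adjusting for sex or age, so a different mix of people in the two quartiles can create or hide the result

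*Combined protocol and SAP*

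**What the plan says.** The primary outcomes (Outcome Measures, A) include, as number 2, "Difference of energy intake (kcal) in high egg consumers as compared to low egg consumers", and as number 4, "Difference of saturated fat (g) intake in high egg consumers as compared to low egg consumers". Number 2 is described as a "Comparison of mean daily energy intake as measured by Remote Food Photography Method (RFPM) between high egg consumers and low egg consumers".

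The third paragraph of the SAP defines high consumers as "individuals in the top quartile based on egg consumption" and low consumers as the bottom quartile, and compares the two "via Welch t-tests or the Wilcoxon test, depending on the distributions of the data". It names no covariate, matching or stratification for this comparison. The Overview gives the number of subjects: "Thus, the total sample size will be 48".

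For the meal-level models and the crossover models the SAP states: "Age, sex, baseline BMI and / or waist circumference will be included in the models as subject-level covariates". The comparison of dietary assessment methods is to be run both with and without those covariates. Hypothesis 3 asks for adjustment; hypothesis 2, which these two outcomes serve, does not mention it.

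The 40-subject proposal appended to the protocol adds one sensitivity analysis for the quartile comparison, a correlation with observed egg intake. It names no covariates either.

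**The concern.** The meal-level contrast, the crossover and the method comparison are wholly or largely within-person, so fixed traits such as sex mostly cancel. The quartile comparison is purely between people who chose their own egg intake. Both sexes are eligible, from 18 to 65 years, with no quota. Adjustment is therefore planned where it matters less and left out where it matters more.

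If one quartile holds more men, or differs in age, part of the difference in intake reflects who is in the group. The appended proposal (Expected results) would explain a higher intake in high egg consumers by the foods eaten with eggs. An imbalance in sex or age could imitate that pattern, and the opposite imbalance could conceal a real one. Two of the six primary outcomes are affected.

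**Working it through.** **Is there a planned figure to reproduce?** Not for this comparison. The only power statement is in the appended proposal: 40 subjects, effect size 0.45, 80% power. A paired or one-sample t-test on all 40 at two-sided 5% gives 79.3%, so the figure reproduces for a within-subject comparison. For 12 vs 12, power at 0.45 is 18.3%, and the difference detectable with 80% power is 1.20 SD.

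**Inputs from the documents.**
- 48 subjects in quartiles: 48 / 4 = 12 per extreme group.
- A yardstick from the cited cohort (appended proposal, B. Background): "men reported greater daily energy intake from 1,870 kcal to 2,372 kcal", so 2,372 − 1,870 = 502 kcal. This is a contrast within men, not a stated design effect.
- Family-wise error rate of 0.05.

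**Assumed inputs, because the documents give none.** Male–female gap 400 to 700 kcal/day; within-sex SD 500 kcal/day; number of men in each quartile as shown.

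**Step 1: bias with no true egg-group difference.** Bias = (difference in share of men) × (sex gap).

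| Men, top vs bottom (of 12) | Difference in share | Bias at 400 to 700 kcal gap | Share of 502 kcal |
|---|---|---|---|
| 7 vs 5 | 2/12 = 0.167 | 67 to 117 kcal | 13% to 23% |
| 8 vs 4 | 4/12 = 0.333 | 133 to 233 kcal | 27% to 46% |
| 9 vs 3 | 6/12 = 0.500 | 200 to 350 kcal | 40% to 70% |

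**Step 2: rejection of a true null.** Simulated Welch tests, nominal two-sided 5%, with the sex mix held fixed. Repeat runs agree to within about one percentage point.

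| Men, top vs bottom | Gap 400 to 700 | Gap 600 |
|---|---|---|
| 7 vs 5 | about 3–4% | 3.7% |
| 8 vs 4 | about 7–10% | about 9% |
| 9 vs 3 | about 12–24% | about 20% |

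A mild imbalance stays below 5% because the Welch standard error includes the spread between men and women within each group. The Wilcoxon test behaved similarly in a separate simulation that drew the mix at random. A regression on all 48 with three egg groups and sex rejects in about 5% in the imbalanced cases.

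The rates depend only on gap divided by SD, here 0.8 to 1.4. They carry over to saturated fat if the sex gap there is of the same relative size.

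**Step 3: the masking direction.** For a true 502 kcal difference with a gap of 600, Welch power is 51% when the sexes are balanced. It falls to 20% and 10% when the bottom quartile has the extra men (4 vs 8 and 3 vs 9). The sex-adjusted contrast on all 48 keeps about 61–67%.

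**Step 4: allowing for multiplicity.** The SAP does not name its procedure. At an illustrative 0.05 / 6 = 0.0083 and a gap of 600, 8 vs 4 and 9 vs 3 reject in about 1.6% and 5.2%. The absolute rates are lower, but still above 0.83%.

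**Step 5: chance imbalance.** If half of all subjects are men and sex is unrelated to egg intake, male counts differ by 4 or more in 15% of samples. Averaged over all such samples, Welch rejects in about 4.9%, so there is no overall inflation.

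**The case against.** The strongest objection is that the imbalance is supposed, not documented. Nothing in the documents shows that men are over-represented among high egg consumers, and if sex is unrelated to egg intake the unadjusted test keeps its 5% on average. This stands: the larger rates above hold only if such an imbalance occurs. It does not remove the point, because the plan offers no protection if one does occur, and a chance imbalance of 4 or more men is not rare.

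Second, a reader might infer that body size is as serious a confounder as sex. The documents do not support this. The same sentence that supplies the 502 kcal contrast says that BMIs were almost the same across egg groups. In a simulated example with balanced sexes, a BMI gap of 0.5 SD raised the false-positive rate only to 5.9%. BMI and waist may also partly result from intake, so forcing them into the only primary model risks over-adjustment.

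Third, a reader might infer that the plan would treat the difference as caused by eating eggs. It does not: the appended proposal regards egg intake as a possible marker of other dietary habits, and hypothesis 2 is worded as a group comparison. An unadjusted difference is a legitimate description of whether high egg consumers eat more. The problem arises when it is attributed to the foods that accompany eggs.

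Finally, primary outcomes 1 and 3 address the accompanying-food hypothesis at meal level with covariates. That is true and lessens the consequence, but outcomes 2 and 4 are primary in their own right.

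**Conclusion.** The concern holds for sex and age: outcomes 2 and 4 rest on an unadjusted, non-randomised comparison of about 12 vs 12, and no adjusted version is planned. The rates of 3–4%, 7–10% and 12–24% rest on an assumed sex gap, SD and sex mix. They show what an imbalance would do and do not predict the trial's error rate. No size was computed for age; the mechanism is the same.

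A reader might infer from the most unbalanced case that these two outcomes cannot be interpreted without the change. The documents do not support that, since they contain no evidence that such an imbalance will occur. This is a should-fix: the remedy is specific and cheap, and the size of the harm is undocumented.

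**What to change.** In the third paragraph of the SAP, make the test for outcomes 2 and 4 a linear regression of 7-day mean energy intake, and separately of saturated fat intake, on egg group (bottom quartile, middle two, top quartile) in all 48 subjects, adjusted for age and sex. Report the adjusted top-minus-bottom contrast. If residuals are skewed, use the Box-Cox transformation that the SAP already provides for its other linear regressions.

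Add a sensitivity model that also includes BMI and/or waist, with the choice fixed in advance, and report the unadjusted difference alongside. This follows the with-and-without approach already planned for the method comparison.

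The cost is a short SAP edit and a few degrees of freedom: five coefficients leave 48 − 5 = 43 residual degrees of freedom. No new data are needed, since age and sex are on the screening form and data sheet and BMI and waist are measured at Visit 1. Under the assumptions above (gap 600, SD 500, balanced sexes), sex adjustment on all 48 raised power for 502 kcal from 51% to 67%. If age and sex explain little of intake, precision would be slightly worse than in the same regression without them.

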## **B. Hypotheses:**

These aims will test the following hypotheses:

1. Meals that include eggs will have higher energy and saturated fat contents as determined by RFPM, compared to corresponding meals (i.e. breakfast, lunch, or dinner) without eggs.
2. As determined by RFPM, individuals of the study sample who will be in the highest quartile in terms of egg consumption in the free-living condition (defined as high egg consumers) will have a higher intake of saturated fat and total energy as compared to individuals who will be in the lowest quartile in terms of egg consumption (defined as low egg consumers).
3. Baseline insulin level, blood glucose level, the Homeostatic Model Assessment (HOMA) index of insulin resistance using fasting glucose and insulin levels, and HbA1C will be positively associated with total EI and saturated fat intake determined by RFPM, even when adjusted for age, sex, BMI and waist circumference
4. Above outcome variables will not be associated with egg intake determined by RFPM.

5. In the randomized partial crossover study, presence of eggs in the breakfast will be associated with a) a greater increase (i.e. both area under the curve and pre-post change) in satiety hormones (i.e. PYY and GLP-1), b) a less profound increase in blood glucose and insulin levels, c) a greater decrease in the hunger hormone (ghrelin) and d) an increase in the area under the curve of metabolic rate when controlled for the content of saturated fat in the test diets.
6. In the randomized partial crossover study, presence of a high amount of saturated fat in the breakfast will be associated with a) a greater increase (i.e. both area under the curve and pre-post change) in satiety hormones (i.e. PYY and GLP-1), b) a less profound increase in blood glucose and insulin levels, c) a greater decrease in the hunger hormone (ghrelin) and d) an increase in the area under the curve of metabolic rate when controlled for the presence of eggs in the test diets.
7. In the randomized partial crossover study, the associations mentioned in hypothesis 5 will be moderated by the presence of a high amount of saturated fat in the diet.
8. Estimates of total EI by RFPM will be significantly greater than EI estimates by 7-day food record and the 24-hour recall in dietary assessment.

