#### **I. Food Record and 24-hour Recall**

Food record will be maintained by each subject for 7-day period (Appendix G). A 24-hour recall will be collected on the day 1 of the 7 days using Automated Self-Administered 24-Hour (ASA24®) Dietary Assessment Tool.

**Visit 1-** The eligible subjects will come to TTU clinic (Tech Plaza rooms 302 and 305) at about 8 AM after 10 hours fast. Here subjects are allowed to take water. After obtaining informed written consent (Appendix C), anthropometric measurements like weight, height, waist and hip circumferences and blood pressure measurements will be taken (Table 4).

Next, pre-prandial blood sampling will be down 30 minutes prior to test breakfast 1. To retrieve blood samples, an IV catheter will be placed by the registered nurse. Blood draws will be continuously done at 30 before and 30, 60, 90, 120, and 180 minutes after breakfast consumption. Pre-prandial blood draw will be done to assess fasting blood glucose, HbA1c, and hormone levels (i.e. serum insulin PYY, GLP1, ghrelin). Post-prandial blood draws will be done to assess blood glucose and hormone levels. Following pre-prandial blood draw, subjects will be asked to assess their hunger and fullness using the visual analog scale (VAS) (Appendix E). The RMR will be tested for each subject, followed by a standardized test breakfast 1, provided a smartphone and trained to photograph their food intake, using the smartphone provided. The subjects will be asked to consume the entire breakfast in 10 minutes. A food frequency

questionnaire (FFQ) (Appendix F) will be given to assess the egg consumption. RMR will be determined 60 and 120 min post breakfast. Blood draws and VAS administration will be continuously done at 30, 60, 90, 120 and 180 minutes after breakfast consumption. After testing is complete at the 180-minute post-breakfast mark, the subject's IV catheter will be removed.

Subjects will take photos of foods before eating and of the leftovers if any with the help of a smartphone using SmartIntake© app for 7-days. Participants will record all meals for the next 7 days in a food record (Appendix G) as well. On the following day (day 1 of 7 days) a 24-hour recall will be done using Automated Self-Administered 24-Hour (ASA24®) Dietary Assessment Tool.

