**Visit 2-** On day 8, participants will be asked to return with 10 hours fast. As in Visit 1, an IV catheter will be placed by the registered nurse in the subject's upper limb to collect blood for blood glucose, and hormones. Blood will be collected for fasting blood glucose levels and insulin levels PYY, GLP1, ghrelin (as described above) 30 minutes prior to the breakfast. They will be randomized to receive test breakfast 2. Blood draws will be continuously done at 30, 60, 90, 120 and 180 minutes after breakfast consumption. Following each blood draw, subjects will be asked to assess their hunger and fullness using the visual analog scale (VAS) (Appendix E). RMR will be determined 30 mins prior and 60 and 120 min post breakfast.

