## **B. Secondary Outcome Measures:**

1. Difference of subjective hunger level compared between different test breakfasts

This will be measured on visit 1 and 2 after providing test breakfasts.

[Time Frame: Changes in scores (arbitrary units AU) from 30 minutes prior to breakfast to 180 minutes after consumption of test breakfasts (Part II of the study)]

2. Difference of subjective satiety level compared between different test breakfasts

This will be measured on visit 1 and 2 after providing test breakfasts.

[Time Frame: Changes in scores (arbitrary units AU) from 30 minutes prior to breakfast to 180 minutes after consumption of test breakfasts (Part II of the study)]

3. Difference of objective hunger compared between different test breakfasts

This will be measured on visit 1 and 2 after providing test breakfasts by measuring serum ghrelin levels.

[Time Frame: Changes in concentration (area under the curve AUC) from 30 minutes prior to breakfast to 180 minutes after consumption of test breakfasts (Part II of the study)]

4. Difference of objective satiety compared between different test breakfasts using serum Glucagon-like peptide-1 (GLP-1) levels.

This will be measured on visit 1 and 2 after providing test breakfasts by measuring serum GLP-1 levels.

[Time Frame: Changes in concentration (area under the curve AUC) from 30 minutes prior to breakfast to 180 minutes after consumption of test breakfasts (Part II of the study)]

5. Difference of objective satiety compared between different test breakfasts using serum Peptide YY (PYY 3-36) levels

This will be measured on visit 1 and 2 after providing test breakfasts by measuring serum PYY 3-36 levels.

[Time Frame: Changes in concentration (area under the curve AUC) from 30 minutes prior to breakfast to 180 minutes after consumption of test breakfasts (Part II of the study)]

6. Difference of HbA1c levels in high egg consumers as compared to low egg consumers  
This will be measured by taking blood on the visit 1.

[Time Frame: Changes in blood concentration (arbitrary units AU) on visit 1 (Part II of the study)]

7. Difference in Homeostasis Model Assessment-Insulin resistance (HOMA-IR) compared between different test breakfasts

This will be calculated using blood glucose and insulin levels.

[Time Frame: Changes in HOMA-IR values (arbitrary units AU) on visit 1 and 2 after providing test breakfasts (Part II of the study)]

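### The Hypothesis 3 and 4 regressions use one baseline fasting value of insulin, glucose and HOMA-IR per subject, although the same fasting sample is drawn again at Visit 2; using both would narrow the intervals at almost no cost

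*Combined protocol and SAP*

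**What the plan says.** Hypothesis 3 predicts positive associations of energy and saturated fat intake with the glycaemic measures, adjusted for age, sex, BMI and waist circumference. It names the outcomes as "Baseline insulin level, blood glucose level, the Homeostatic Model Assessment (HOMA) index of insulin resistance using fasting glucose and insulin levels", plus HbA1c. Hypothesis 4 covers the same outcomes: "Above outcome variables will not be associated with egg intake determined by RFPM".

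The SAP's method is this: "Linear regression models will be constructed to examined the associations between a) total EI, b) saturated fat intake and c) egg intake". Such a model is ordinary regression with one outcome value per subject; where the SAP expects repeated data it specifies mixed models. Its outcome list for these models reads "each of i) baseline insulin level, ii) blood glucose level, iii) HOMA-IR, and iv) HbA1C level". In that list the word baseline attaches to insulin only, and no visit is named.

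The fasting sample is taken twice:

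- Visit 1, after a 10-hour fast and 30 minutes before breakfast: "Pre-prandial blood draw will be done to assess fasting blood glucose, HbA1c, and hormone levels".
- Visit 2: "On day 8, participants will be asked to return with 10 hours fast". Then, again 30 minutes before breakfast: "Blood will be collected for fasting blood glucose levels and insulin levels".

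Table 3 marks glucose and insulin at both visits and HbA1c at Visit 1 only. The Secondary Outcome Measures agree on HbA1c: "This will be measured by taking blood on the visit 1". No section averages the two fasting values or models them jointly for Hypotheses 3 and 4.

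**The concern.** A single fasting insulin, glucose or HOMA-IR value is the subject's usual level plus day-to-day variation. That variation adds residual variance to the regression and widens the interval for each intake coefficient. A second sample would reduce it, and the protocol already pays for one.

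For Hypothesis 3 the cost is power. For Hypothesis 4 the cost is different: the hypothesis predicts no association, so a noisier outcome makes a non-significant result easier to obtain and less informative. A no-association claim about eggs is close to the study's central message, and it needs the narrowest interval the data can give.

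Precision is already limited. The only power text is in the 40-subject research proposal bound into the file. The current 48-subject plan gives no power for these regressions and also commits to family-wise error control.

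**Working it through.** **The plan's own figure.** The appended proposal states that 40 subjects give 80% power for a correlation of 0.43 at alpha 0.05. By Fisher's z, the detectable r is tanh[(1.960 + 0.842)/√(40 − 3)] = 0.431, so the figure reproduces with a two-sided test. With the current 48 subjects it is tanh[2.802/√45] = 0.395.

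**Inputs for the comparison**

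- n = 48 (Study Design, Overview).
- Two-sided alpha 0.05, unadjusted and without covariates.
- Single-sample reliability R, the between-subject share of the variance in one fasting value. The documents do not give it; I assume 0.6 to 0.95.
- True correlation 0.45 between intake and the subject's usual level. This is also an assumption. The proposal's 0.45 is an effect size; its correlation is 0.43.
- Day-to-day errors at the two visits are taken as independent.

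**Formulas**

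- Reliability of the mean of two samples: R₂ = 2R/(1 + R).
- Gain in effective sample size: R₂/R = 2/(1 + R).
- Outcome variance of the mean relative to one sample: (1 + R)/2. When the true association is near zero, interval width scales with its square root.
- Observed correlation: 0.45√R with one sample, 0.45√R₂ with two.
- Power: Φ[atanh(r)·√45 − 1.960].

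**Worked case, R = 0.6.** R₂ = 1.2/1.6 = 0.75, and the gain is 0.75/0.6 = 1.25. The observed correlation goes from 0.349 to 0.390. Power goes from Φ(2.441 − 1.960) = 68.5% to Φ(2.760 − 1.960) = 78.8%.

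| R | R₂ | Gain in effective n | Interval width, null case | Power, one sample | Power, two |
|---|---|---|---|---|---|
| 0.60 | 0.75 | 25% | 11% narrower | 69% | 79% |
| 0.70 | 0.82 | 18% | 8% narrower | 76% | 83% |
| 0.85 | 0.92 | 8% | 4% narrower | 84% | 87% |
| 0.95 | 0.97 | 3% | 1% narrower | 88% | 89% |

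**Simulation check.** With n = 48, 20,000 runs and a single-visit correlation of 0.395, simulated power rose from 80.2% to 91.5% at R = 0.5, from 81.1% to 87.3% at 0.7, and from 80.8% to 83.1% at 0.9. The Fisher approximation gives 80% rising to 91%, 87% and 82%.

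**Sensitivity to the plan's error control.** The SAP states no multiplicity method. Suppose Bonferroni over 12 tests (3 exposures × 4 outcomes) and four covariates, so that √45 becomes √41 and alpha becomes 0.05/12. Power is then 30% rising to 41% at R = 0.6, and 48% rising to 54% at R = 0.85. Absolute power falls well below the table, but the gain remains.

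**The case against.** The strongest reply is that nothing here is an error. Regressing a baseline value on intake is valid and conventional, and Aim 4 and Hypothesis 3 name baseline levels as the target. These associations are not among the listed primary or secondary outcomes. The gain cannot be sized from the documents and is slight if reliability is 0.9 or more. All of that stands, and it sets the weight of the point: an optional improvement.

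Several stronger readings are tempting, and the documents do not support them.

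- *A reader might infer that the single sample biases the results.* Random error in the outcome weakens the observed correlation and widens intervals, but it does not shift a regression slope.
- *A reader might infer that every association suffers.* HbA1c is measured once, so there is nothing to average.
- *A reader might infer that the SAP expressly restricts these models to Visit 1.* It names no visit. Visit 1 is the natural meaning of baseline, no more.
- *A reader might infer that Visit 1 is mistimed because it precedes the recorded intake.* The Significance section treats the photographed week as a measure of usual diet, so an adjacent fasting value on either side is a reasonable match. Taken alone, the timing argument would favour Visit 2 rather than the mean. The narrower point is that the week lies between the samples, so neither has a special claim.
- *A reader might infer that Visit 2 is a pure repeat of baseline.* One test breakfast, seven days of photographing and recording all food, and a 24-hour recall come between the two. Self-monitoring could change intake, so a shift between visits is possible and the analysis should allow for it.

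A plain mean for some subjects and Visit 1 alone for others would also give unequal error variances. That is a reason to prefer a mixed model, not to discard the second sample.

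**Conclusion.** The point holds as a low-cost gain in precision. Hypotheses 3 and 4 use one fasting value per subject where the protocol collects two under the same fasting conditions, and the second could tighten the insulin, glucose and HOMA-IR associations. With independent errors, the gain is positive for any reliability below 1: about 25% more participants at 0.6, falling to 3% at 0.95. The power figures also depend on the assumed correlation of 0.45 and on unadjusted alpha without covariates, so they show the size of the improvement, not the power this plan would deliver.

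Hypothesis 4 benefits most, but only in interval width. Averaging does not make a non-significant result evidence of no association; that would need a margin, which the SAP does not state.

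**What to change.** Amend the SAP before analysis so that, for Hypotheses 3 and 4:

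- fasting glucose, insulin and HOMA-IR from both visits are used, on the log scale if skewed, with HOMA-IR calculated at each visit;
- the two values enter either as the subject mean or, preferably, as repeated outcomes in a mixed model with a random subject intercept and a visit term, which keeps subjects who miss Visit 2 and handles their larger error variance;
- Visit 1 alone is reported as a sensitivity analysis, with baseline defined explicitly as the Visit 1 fasting sample for all three measures;
- HbA1c stays as the single Visit 1 value.

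The cost is a sentence or two. No new blood, assay or visit is needed, and lmerTest is already the SAP's mixed-model package. The price is interpretive: the outcome is no longer strictly baseline, because Visit 2 follows a test breakfast and a week of food photography and recording. The visit term absorbs an average shift, and the Visit 1 analysis shows whether the conclusions depend on the second sample. Fixing the rule in advance also removes any choice between visits after the results are seen.
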